After completion of the AET+ or control regimens, subjects will undergo the follow up research test battery. The follow up battery consists of echocardiogram, pulmonary function test, arterial occlusion muscle oxygenation test, 6MWT, tCPET, and questionnaires identical to those included in the battery at baseline. Subjects in the control group will subsequently participate in a 10-week AET regimen identical to AET+ except without the educational lectures, since participation in the lectures was completed as the control condition. A second identical, follow up test battery will be completed by this group after the crossover AET regimen is completed. After completion of their AET+, subjects will be contacted monthly with regard to continued exercise habits, the frequency, length, and severity of hospitalizations, or acceptance to a lung transplant waiting list. Mortality will also be assessed at this time.

**Specific Aim 1:** "Determination of the Influence of AET+ on PWC in Patients with ILD".

The main outcome variable for this project is 6MWT distance, which is the most frequently used measure of physical performance for evaluating patients with ILD and other advanced lung diseases. A minimal clinically important difference (MCID) for 6MWT distance has been determined to be approximately 30 meters in ILD. Additional measures of PWC used in this study are peak WR on the tCPET, and performance and perceived fatigability as measured by a modification of the method used by Schnelle and coworkers in an older cohort. We will measure all 4 of these variables at baseline and after the AET+ and control regimens, as well as after the crossover regimen. We hypothesize that:

- 1.1. An increase in 6MWT distance of at least 30 meters longer than control will be observed after AET+.
- 1.2. A significant increase in peak WR will be observed after AET+ compared to control.
- 1.3. A significant decrease in performance fatigability will be observed after AET+ compared to control.
- 1.4. A significant decrease in perceived fatigability will be observed after AET+ compared to control.

- 1.5 In the Sub-study on Crossover we hypothesize that AET will result in improvements over baseline in all of the variables of interest including 6MWT, peak WR, and performance and perceived fatigability that are similar to AET+.

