## Research Tests

Once the inclusion and exclusion criteria have been satisfied, the enrolled subject will undergo the following tests:

**Six-minute Walk (6MWT) and Fatigability Tests:** Subjects will rest in a seated position for a minimum of 30 minutes during which they complete the study questionnaires prior to beginning the 6MWT. Resting blood pressure, pulse rate, and oxygen saturation will then be recorded in the seated position. The subject will then be asked to stand and instructed to walk as far as possible around a pre-measured walking course over a time period of six minutes. Oxygen saturation and pulse rate will be measured throughout the test using a portable pulse oximeter. Oxygen saturation, pulse rate, rating of perceived dyspnea, rating of perceived exertion will be recorded upon completion of each lap of the walking course. Distance covered will be recorded at 1.5 minutes and the end of 6 minutes. The Fatigue/Fatigability Scale will be completed before the test begins and immediately after. Immediately upon completion

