of the six minutes the subject will be asked to stop and immediate post-exercise pulse rate and oxygen saturation will be recorded. The subject will then be asked to rest in a seated position and pulse rate will be recorded during each minute of recovery for a total of ten minutes to evaluate the subject's ability to recover from intense activity. Supplemental oxygen will be provided for those patients that require supplemental oxygen while exercising and/or resting. Those subjects requiring supplemental oxygen will be provided supplemental oxygen with the same delivery device and flow pre/post intervention to maintain consistency. The target endpoint for this test is the completion of the six minutes of walking however symptomatic endpoints for stopping the tests will be those recommended by the American College of Sports Medicine. Additionally should any subject's oxygen saturation desaturate to  $\leq 80\%$  the patient will be required to stop walking at this point with or without the presence of symptoms of severe dyspnea. The patient will rest, while the timer continues to run, until oxygen saturation returns to baseline values or above 90% at which point the patient will resume walking again. The main outcome variable for this project is the change in 6MWT distance from before to after the AET+ and control regimens. The performance fatigability index will be calculated as the ratio of the 1.5-minute walking speed to the walking speed calculated over the entire 6 minutes of the test divided by the total distance covered on the test. The perceived fatigability index will be calculated by having the subject rating their feeling of tiredness prior to the 6MWT and measuring the change in tiredness after the 6MWT. The change in tiredness divided by the total distance walked will be computed as the perceived fatigability index.

Blood glucose of diabetic patients will be monitored before and after testing, and as clinical necessary. Testing will be performed by qualified staff using NIH glucometer or patient's own glucometer. In order to use patient's own glucometer, it must first be validated for accuracy through the NIH Department of Laboratory Medicine.

Fatigue Scale Items (Use before Walking Test)	Score	Fatigability Scale Items (Use After Walking Test)
Extremely Tired	7	Extremely More Tired
Somewhat Tired	6	Somewhat More Tired
A Little Tired	5	A Little More Tired
Neither Tired Nor Energetic	4	Neither More Tired Nor More Energetic

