### **Analysis**

Our statistical model for specific Aims 1-3 will compare variables of interest between and within the AET+ and CON groups at baseline and post-intervention with a 2-way mixed model analysis of variance (2-way ANOVA). Should there be baseline differences in the specific variable of interest or in demographic characteristics, we will use an analysis of covariance (ANCOVA) to control for the group equality, but the study will be powered under the assumption that no informative covariates are identified and using 6MWT as the primary outcome.

In Specific Aim 1 we will test the hypothesis that AET+ will improve scores on measures of PWC. The dependent variables for this Aim include total distance covered and fatigability index on the 6MWT, and peak WR achieved on the tCPET. 6MWT distance is the primary outcome variable for this RCT and thus our project is powered on the sample size estimated to achieve a significant outcome on this variable (See Sample Size below).

In Specific Aim 2, we will test the hypothesis that after AET+, significant increases in AT-time and muscle oxygenation will be observed over CON. The main dependent variables for this aim are AT-time and measures of muscle oxygenation which include [Tot-Hb], [O2-Hb], [H-Hb], and StO2 measured during tCPET and muscle arterial occlusion cuff tests. Additional dependent variables will include Qt and its components HR and SV measured during tCPETs.

In Specific Aim 3 we will test the hypothesis that patients will report decreased fatigue severity, increased physical activity, and improvements in other HRQoL. The dependent variable score for fatigue severity will be the Fatigue Severity Scale score. The dependent variable score for physical activity will be the Human Activity Profile maximum and average scale scores, and the scores for HRQoL will be composite and domain scores for the SGRQ-I, SF-36v2, and K-BILD.

In the crossover sub-study, we will determine if AET+ induces significant improvements in the variables of interest in the CON group. For this analysis we will use repeated measures ANOVA’s to determine differences in the variables of interest among baseline, 10-week post control, and 2-week post crossover AET data points. Dependent variables will be those in each of the specific aims characterized above.

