In Specific Aim 4, relationships between the post-study physiological variables and health outcome variables will be determined using Pearson product moment correlations and appropriate nonparametric procedures.

In all of the analyses, statistical significance will be interpreted as the probability of making a type 1 error equal to or less than 5% ( $p \leq 0.05$ ).

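### The performance fatigability index counts a staff-imposed desaturation rest as walking time, so a walker who never slows can score as more, or less, fatigable

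*Combined protocol and SAP*

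**What the plan says.** All the rules sit in the protocol's Research Tests section, under the heading for the 6MWT and fatigability tests.

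- **Index.** "The performance fatigability index will be calculated as the ratio of the 1.5-minute walking speed to the walking speed calculated over the entire 6 minutes". That ratio is then divided by the distance walked in the whole test. Both speeds are over clock time.
- **Forced stop.** At a saturation of 80% or lower, "the patient will be required to stop walking at this point with or without the presence of symptoms of severe dyspnea".
- **Clock.** "The patient will rest, while the timer continues to run, until oxygen saturation returns to baseline values or above 90"%. No maximum rest length is given.
- **Recording.** "Distance covered will be recorded at 1.5 minutes and the end of 6 minutes". Saturation is monitored throughout and written down at each lap. The section does not ask for the start or end of a forced rest.

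Under Specific Aim 1, hypothesis 1.3 reads: "A significant decrease in performance fatigability will be observed after AET+ compared to control". The Analysis section lists "total distance covered and fatigability index on the 6MWT" among the Aim 1 dependent variables, with no rule for walks that contain a stop. By contrast, the Exercise Training section stops the session timer during rest breaks.

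**The concern.** Early speed over whole-test speed is a measure of slowing. A standstill ordered by staff from an oximeter reading, and explicitly not tied to symptoms, is not slowing. With the clock running, however, it lowers whichever speed it falls in. The score then depends partly on whether and when saturation crossed a limit.

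Performance fatigability is one of four Aim 1 measures and has its own hypothesis. Forced stops are foreseeable. In the preliminary cohort 38% needed supplemental oxygen, and the Exercise Training section provides for patients who come to need oxygen during training. That section also holds the post-training tests to the baseline oxygen device and flow. A patient whose oxygen need has grown is therefore retested on the old supply, which is one route to new stops at follow-up. With 30 patients per arm and an analysis of means, a few badly shifted scores could matter.

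**Working it through.** The plan gives no figure for this index, so there is nothing to reproduce. The check is algebra on the written definition.

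**Inputs.** The mean baseline distance is 385 m (Sample Size section). A constant-speed walker therefore has s = 385/6 = 64.2 m/min. One forced rest starts at minute t and lasts r minutes. The documents give no rest lengths, so r from 0.5 to 2 min is an assumption.

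**Definition.** Ratio R = [d(1.5)/1.5] / [d(6)/6], and index = R/d(6), with d(6) = s(6 − r). Without a stop, R = 1.00 and the index is 1/385 = 0.00260.

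**Formulas.** The relative index is the index divided by its no-stop value, which equals R × 6/(6 − r).

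- Rest starts at or after 1.5 min: R = 6/(6 − r).
- Rest begins and ends by 1.5 min: R = [(1.5 − r)/1.5] × 6/(6 − r).
- Rest straddles 1.5 min: R = 4t/(6 − r), and relative index = 24t/(6 − r)².

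| Rest starts (min) | Length (min) | Ratio R | Written index against no stop |
|---|---|---|---|
| 1.5 or later | 0.5 | 1.09 | +19% |
| 1.5 or later | 1.0 | 1.20 | +44% |
| 1.5 or later | 1.5 | 1.33 | +78% |
| 1.5 or later | 2.0 | 1.50 | +125% |
| 0.5 | 0.5 | 0.73 | −21% |
| 0.5 | 1.0 | 0.40 | −52% |
| 1.0 | 1.0 | 0.80 | −4% |
| 1.25 | 1.5 | 1.11 | +48% |

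**When a straddling rest lowers the score.** R < 1 requires r < 6 − 4t. The index falls below its no-stop value only if r < 6 − √(24t). For t = 1.0 these limits are 2.0 and 1.10 min. For t = 1.25 they are 1.0 and 0.52 min.

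**Scale.** A 30 m gain at even pace with no stop changes the index by 385/415 − 1 = −7.2%. If a share p of an arm newly has a 60 s late stop at follow-up, the arm mean returns to its starting value when (385/415)(1 + 0.44p) = 1, which gives p = 0.0779/0.44 = 18%. The corresponding share is 41% for 30 s rests and 6% for 2 min rests. These are break-even shares, not estimates.

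**Effect of changing the time base.** With both speeds taken over walking time, R = 1.00 in every row. The index is still divided by a distance that the rest shortens, so it remains at 6/(6 − r): +9%, +20% and +50% for 0.5, 1 and 2 min. For the 60 s stop at minute 1.0, the index would go from −4% to +20%. Changing the time base therefore repairs the ratio but not the distance-divided index.

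**Reading of the formula.** The sentence could also be parsed as v1.5/(v6/d(6)). Since v6 = d(6)/6, that reduces to 6 × v1.5, which measures no slowing at all. The reading used here is the natural one.

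**The case against.** Several counter-arguments have force.

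- **No bias is demonstrated.** The stopping rule applies to both arms, and oxygen delivery is held constant between visits. The documents do not say how often saturation reaches 80% during the walk. A reader might infer that the AET+ versus CON comparison is biased. The documents support only that it could be, in a direction that cannot be fixed. This stands.
- **Early stops do not always reverse the score.** A reader might infer that any stop before minute 1.5 makes the patient look less fatigable. That is certain only if the rest also ends by then. The −52% case further needs a fall to 80% or lower within 30 s of starting, in patients who must hold at least 90% at rest, followed by recovery within 60 s. This stands.
- **The true ratio of 1.00 is assumed.** A patient who desaturated might have slowed anyway, which would make the error smaller than shown. Pace after an enforced rest may also understate slowing. Both points stand as limits.
- **Leaving out stopped walks conditions on an event after randomisation** that training may itself affect. This stands, so such an analysis can be supportive only.
- **It is one outcome on which the trial is not powered.** This is true and limits the weight of the point. It does not supply the missing scoring rule.

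**Conclusion.** The point holds as a defect in the definition of one non-primary outcome. The written index treats a forced rest as walking time. For a constant-speed walker and a 60 s rest, that gives a ratio of 1.20 (index +44%) if the rest comes after minute 1.5, and 0.40 (index −52%) if it runs from minute 0.5 to 1.5. A straddling rest can raise or lower the score. These sizes rest on an even-paced walker and assumed rest lengths.

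At group level, forced stops could add outliers to the hypothesis 1.3 comparison or bias it. Neither size nor direction can be stated, because stop frequency is not given.

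A reader might extend the criticism to 6MWD. The documents do not support that. A forced rest does shorten the distance, but distance covered in a fixed six minutes includes any rest by definition. A ratio meant to isolate slowing should not.

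**What to change.** Leave the stopping rule and 6MWD as they are. Then:

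1. Record the start and end clock time of every saturation-forced rest on the 6MWT sheet.
2. Compute early speed as d(1.5)/(1.5 − forced rest within the first 1.5 min) and whole-test speed as d(6)/(6 − total forced rest). Keep voluntary slowing and voluntary stops in the time base.
3. Test hypothesis 1.3 on the ratio of these two speeds. Report the index with the written division by total distance alongside, noting that this division still carries the forced rest (+20% for 60 s).
4. Report the number of walks with a forced stop by arm and visit. Repeat the comparison without those walks as a sensitivity analysis only.

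The cost is two clock times per forced rest, a revised definition of the index, one table of counts and one extra analysis. There are two downsides. The Sample Size section refers to completion rates to date, so some walks have already been done, and the protocol does not say that a continuous oximetry trace or lap times are stored. Rest times for those walks may not be recoverable, and the walks should be flagged. Pace after an enforced rest may also understate slowing, which the report should acknowledge.

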**Specific Aim 2:** “Characterization of the Cardiorespiratory Adaptation to AET in Patients with ILD.” Measures of cardiorespiratory capacity are often influenced by subjective factors such as motivation and confidence. Our measures of cardiorespiratory capacity in this project are AT-time, and muscle oxygenation capacity. Neither of these physiological measures is influenced by subjective factors. We will measure AT-time during tCPET and muscle oxygenation by arterial occlusion testing at baseline and after the AET+ and control regimens. We will also measure Qt, peak VO2, PETO2 and PETCO2 during tCPETs at baseline and after the AET+ and control regimens. We will measure all of the variables again after the group initially completing the control regimen completes the crossover AET regime. We hypothesize:

- 2.1. After the AET+ regimen, AT-time will be significantly prolonged over controls.
- 2.2 After AET+, a significant increase in muscle oxygenation capacity will be observed over controls.
- 2.3 Qt, peak VO2, PETCO2 and PETO2 will remain unchanged following both AET+ and control regimens.
- 2.4 In the Sub-study on Crossover we hypothesize that AET will result in improvements over baseline in all of the variables of interest including AT-time and muscle oxygenation that are similar to AET+. We also hypothesize that Qt, peak VO2, PETO2 a PETCO2 will remain unchanged over baseline after AET.

**Specific Aim 3:** “Determination of the Influence of AET on Patient-reported Measures of Fatigue, Physical Activity, and Other HRQoL Domains in Patients with ILD.” We will use the Fatigue Severity Scale (FSS) to assess fatigue severity, Human Activity Profile (HAP) to assess participation in physical activities, SF-36v2 to assess general HRQoL, Profile of Mood States (POMS) to assess changes in mood, and Kings Brief Interstitial Lung Disease Health Status Questionnaire (K-BILD) to assess HRQoL specific to ILD. We will also use the St. Georges Respiratory questionnaire to assess HRQoL specific to IPF. Subjects will answer the questionnaires before and after the AET+ and control regimens. Subjects in the group receiving the control regimen will again answer the questionnaires after completing the crossover AET regimen. We hypothesize

- 3.1. After AET+, fatigue severity will be diminished over control.

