Near Infrared Spectroscopy: Muscle microcirculatory reactivity and muscle tissue oxygen extraction will be measured by spatially resolved near infrared spectroscopy (NIRS). Near Infrared (NIR) light is emitted into the muscle tissue at known distances from a sensor by a NIR emitting diode. The amount of NIR light returning to a photo-sensing diode is measured and processed according to two wavelengths of the NIR spectrum, and the absorption and scattering coefficients of the medium are calculated. Oxygenated ([O2-Hb]) and de-oxygenated hemoglobin ([H-Hb]) concentrations are then determined as an interaction between their corresponding wavelengths and the amount of light that is collected by the NIR sensors. These calculations are however influenced by oxygenated and deoxygenated myoglobin concentrations, which in this project may introduce some conservative bias. In general, oxy and doxy hemoglobin and myoglobin dynamics tend to fluctuate in the same direction, often making the influence of myoglobin on the analysis superfluous. Myoglobin concentration in muscle is small compared to hemoglobin and most accounts have indicated that the myoglobin signal accounts for less than 10% of the total NIR absorption, rendering its influence less confounding. Spatially resolved measurements of total tissue hemoglobin, ([Tot-Hb], [O2-Hb] and [H-Hb]) are absolute measures and desaturation rates are time constant based kinetic indices. A single infrared transducer containing both infrared laser emitting diodes and frequency specific light sensors will be attached to the gastrocnemius muscle and worn by the subjects during the symptom limited treadmill exercise test. The lasers are cool lights and will not be felt by the subjects. Reports of burns or other tissue damage occurring with the use of these devices are not found. NIR measurements of muscle oxygenation will be made during tCPET as well as during an arterial occlusion test.

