Bioelectrical Impedance Plethysmography: Measurements of cardiac output will be made using a bioelectrical impedance cardiograph (ZCG). Silver/silver chloride electrodes are placed on the subjects' chests at known distances and the electrocardiographically-gated rate of change in electrical conductance is measured. This produces a waveform that is the inverse of the pulse tracing obtained from Doppler ultrasound analyses. The first derivative of the waveform is then used to estimate cardiac output. This can occur because air in the lung provides no resistance to electrical current leaving impedance to vary only with changes in fluid volume. Additional data accurately obtained by ZCG includes pre-ejection period, dz/dt, which is analogous to the dv/dt of the Doppler blood flow graph, the dz/dt second derivative, an index of cardiac inotropy analogous to Doppler measured peak ascending aortic acceleration, and left ventricular ejection time. Changes in total peripheral resistance can be determined when brachial artery blood pressure is measured ( $TPR = [1/3(SBP-DBP)+DBP]/\text{cardiac output}$ ).

Arterial Occlusion Muscle Oxygenation Capacity Test: NIR light source and receiving sensors will be placed on the belly of the dominant gastrocnemius muscle to record muscle oxygen-hemoglobin flux. A blood pressure cuff will be placed around the distal hamstrings of the dominant leg. Using a Hokanson® rapid inflation vascular testing system, the cuff will be rapidly inflated to a pressure that totally occludes blood flow into the gastrocnemius, typically between 60 and 80 mmHg above systolic pressure. The occlusion will be maintained for up to 10 minutes and tissue saturation will be measured over the time course. The tissue saturation index will be calculated as  $STI = [O_2-Hb] / \text{Tot-Hb}$ . The rate of decline in STI will be the main muscle tissue saturation measure.

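### Three sections of the plan disagree on which muscle-oxygenation measure, from which test, decides hypothesis 2.2

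*Combined protocol and SAP*

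**What the plan says.** Three places bear on the muscle-oxygenation claim of Aim 2.

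- **Study Design and Methods, Specific Aim 2.** The aim will measure "muscle oxygenation by arterial occlusion testing at baseline and after the AET+ and control regimens". Hypothesis 2.2 then reads "After AET+, a significant increase in muscle oxygenation capacity will be observed over controls". It names no variable and no decision rule.
- **Research Tests, Arterial Occlusion Muscle Oxygenation Capacity Test.** STI is defined as [O2-Hb] divided by Tot-Hb. On timing, "The occlusion will be maintained for up to 10 minutes and tissue saturation will be measured over the time course". One summary is then singled out: "The rate of decline in STI will be the main muscle tissue saturation measure".
- **Analysis, Specific Aim 2.** "The main dependent variables for this aim are AT-time and measures of muscle oxygenation which include [Tot-Hb", and the list continues with [O2-Hb], [H-Hb] and StO2. All are "measured during tCPET and muscle arterial occlusion cuff tests". The rate of decline is not named.

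Two further statements matter. The Near Infrared Spectroscopy paragraph separates the two kinds of quantity: the concentrations "are absolute measures and desaturation rates are time constant based kinetic indices". The Analysis section closes by saying that in all analyses "statistical significance will be interpreted as the probability of making a type 1 error equal to or less than 5" percent. No hierarchy, multiplicity adjustment or rule for combining results is given for Aim 2.

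**The concern.** Someone analysing the trial from the Analysis section would test a different set of quantities, in a different set of tests, from someone following the occlusion-test paragraph. Both could say that they had followed the plan. Hypothesis 2.2 is one of the two main claims of Aim 2 and carries the argument that training works through oxygen extraction in muscle. With several main variables at 0.05 each and no rule, a reader of the results could not tell a planned finding from a selected one.

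The choice of test matters too. Specific Aim 2 favours muscle oxygenation because it is held to be free of motivation and similar influences. The treadmill test ends at volitional exhaustion under staff encouragement, and Informational Gaps warns that measurements made at that point may reflect motivation. The Data and Safety Monitoring Plan says that blinding of study personnel cannot continue after randomization. Giving treadmill near-infrared variables main status may therefore weaken the plan's own reason for choosing this outcome.

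The crossover sub-study takes its dependent variables from the specific aims, so it inherits the ambiguity.

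**Working it through.** **The sections side by side**

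| Place | Quantity | Test |
|---|---|---|
| Specific Aim 2 | muscle oxygenation, not specified further | occlusion only |
| Occlusion-test paragraph | rate of decline in STI | occlusion |
| Analysis, Aim 2 | [Tot-Hb], [O2-Hb], [H-Hb], StO2 | treadmill and occlusion |

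The Analysis gives 4 variables × 2 tests = 8 comparisons. Restricted to the occlusion test, as Specific Aim 2 implies, there are 4. The occlusion-test paragraph gives 1.

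**The plan's own figure.** The only figure bearing on hypothesis 2.2 is the 5% threshold. One test at that level gives 1 − (1 − 0.05) = 0.05. The power figures under Sample Size concern 6MWT and do not enter here.

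**If any one significant result were enough and nothing were truly different.** Under independence the chance of at least one false positive is 1 − 0.95^k.

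- k = 4: 1 − 0.95^4 = 0.185
- k = 8: 1 − 0.95^8 = 0.337

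**Allowing for correlation.** The documents give no correlations, so these are assumed. With k two-sided normal tests sharing a common correlation r (400,000 draws):

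| r | k = 4 | k = 8 |
|---|---|---|
| 0.3 | 17.4% | 29.9% |
| 0.5 | 15.7% | 25.1% |
| 0.7 | 12.9% | 19.1% |
| 0.9 | 9.4% | 11.9% |

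**Respecting the algebra.** A second simulation built in the links: total = oxygenated + deoxygenated, and saturation = oxygenated / total. It used two tests, 30 patients per arm, no true effect, and a t test on change (with two time points, the same test as the group-by-time term of the planned ANOVA). The assumed correlation between oxygenated and deoxygenated signals ran from −0.8 to 0.5, and between the two tests from 0 to 0.9, with 8,000 trials per setting.

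- Four variables in one test: 11.6% to 14.0%
- All eight: 16.9% to 25.2%

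**Direction.** Hypothesis 2.2 predicts an increase. Counting only one direction roughly halves the common-correlation figures: for k = 8 at r = 0.5, 12.5% against 25.1%. Applying one half to the linked-variable results gives about 6–7% for four and 8–13% for eight. The matching figure for one measure is 5% / 2 = 2.5%. This halving is approximate, because the Analysis gives no favourable direction for any of the four variables.

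**If the whole set were kept.** Bonferroni levels would be 0.05/4 = 0.0125 or 0.05/8 = 0.00625 per comparison.

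**The case against.** A fair defence is that the sections are incomplete rather than opposed. StO2 is not defined, but it is most naturally the same saturation as STI, and the Analysis also lists that ratio's numerator and denominator. What is missing is the summary statistic. The Analysis gives no summary for any near-infrared signal, its list is worded as open-ended, and the occlusion paragraph could be read as supplying the summary for that test. This is also a secondary aim of a small phase 2 trial that is powered on 6MWT alone.

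Much of that stands, and it rules out several stronger readings.

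- A reader might infer that the plan lets hypothesis 2.2 be claimed on any of eight results. No such rule is written; it is only left open. Specific Aim 2 supports a count of four.
- A reader might quote 34% as the error rate. That needs independence, which a ratio, its components and their total cannot have.
- A reader might say that the Analysis replaces STI with four unrelated variables. The probable identity of StO2 with STI argues against that.
- A reader might take the pilot's lack of a significant rise in total hemoglobin/myoglobin as a reason to discard [Tot-Hb]. Preliminary Results used that null as part of a pattern pointing to extraction rather than delivery.

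The defence does not remove the conflict. The rate of decline is still absent from the Analysis, an open-ended list widens the choice, and the treadmill measurements have main status in one section but no place in the Specific Aim 2 statement of how muscle oxygenation will be measured.

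**Conclusion.** The inconsistency is real and should be corrected. Specific Aim 2, the occlusion-test paragraph and the Analysis do not agree on the measure and test that decide hypothesis 2.2, and nothing in the plan sets an order among them.

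The size is conditional on one significant variable being accepted as support. On that condition the two-sided false-positive chance is about 12–14% for four occlusion variables and about 17–25% for eight, against 5% for one. The inputs are assumed correlations and 30 patients per arm. A common correlation as high as 0.9 would bring the figures down to 9.4% and 11.9%, still above 5%. The 6MWT primary analysis and its power are untouched, and so is the separate AT-time claim in hypothesis 2.1.

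**What to change.** Amend the Aim 2 paragraph of the Analysis, consistent with Specific Aim 2 and the occlusion-test paragraph, so that hypothesis 2.2 is tested once, on the rate of decline in STI during arterial occlusion. In the same amendment:

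- define StO2 and state whether it is STI;
- state the estimator of the rate and the part of the occlusion it covers, since the Near Infrared Spectroscopy paragraph describes time-constant indices while the occlusion paragraph says only that a rate is used, over an occlusion of variable length;
- state which direction counts as improvement;
- label the other near-infrared variables, and all near-infrared measurements from the treadmill test, as supportive, with no stand-alone claim for hypothesis 2.2;
- apply the same rule to the crossover sub-study.

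This must be settled before results are examined. If the sponsor prefers to keep a set of measures, naming the set and dividing alpha across it would also control the error.

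No new measurement is needed. The cost is the amendment and one scientific decision about the estimator. Hypothesis 2.2 would then rest on a single measure, and patients with severe Raynaud's, who do not take the occlusion test, would not contribute to it.
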